5. PROCEDURES

Potential subjects will be identified through multidisciplinary lung tumor board, consults, and the radiation oncology clinic. Consent will be obtained prior to initial radiotherapy treatment simulation. One biopsy site is adequate for multiple sites of thoracic disease, as the primary endpoint of the study is the assessment of normal lung tissue response to delivered radiation.

5.1. Baseline Standard of Care Assessments

- 5.1.1. **4DCT.** For standard of care radiation treatment planning
- 5.1.2. **Pulmonary function tests.** Include spirometry, diffusion capacity (DLCO), and lung volumes (FEV, FEV1)

5.2. Baseline Research Assessments

- 5.2.1. **4DCT.** This is ordered in addition to the standard 4DCT performed for RT-simulation
- 5.2.2. **Patient self-assessment.** Assessment is based on a modified Borg scale, which has a history of use in pulmonary labs, with a scale of 1 (resting comfortably in a chair with no effort) to 10 (the most exertion and difficult breathing ever experienced)
- 5.2.3. **RTOG defined acute toxicity evaluation.** Evaluate both lung and esophageal toxicity (Appendix B)
- 5.2.4. **RTOG late toxicity evaluation.** Evaluate lung, esophageal, skin, subcutaneous tissue, spinal cord, heart, and bone (Appendix C)
- 5.2.5. **Constitutional assessment:** quantify nausea, vomiting, diarrhea and other symptoms prior to initiating chemoradiation and any medications used for these symptoms

5.3. 4-Dimensional Computed Tomography (4DCT) Imaging

4DCT imaging is performed at simulation (treatment planning) in all patients. This first 4DCT is clinically indicated for radiation simulation as a standard procedure. This clinical imaging data will also be used for research in this protocol to evaluate the biomechanical tissue elasticity of the lungs. Lung tissue elasticity is being used as a surrogate for ventilation, which in turn is a component of pulmonary function. Because the goal of the research arm is to reduce pulmonary function damage, changes in lung tissue elasticity will be quantified using 4DCT and it's essential the changes observed be distinguished from random changes in our measurement. Consequently, each subject will receive two 4DCT scans at each time point in order to quantify the repeatability of the measure of tissue elasticity and to demonstrate the changes following RT are greater than the expected variation from the procedure itself. The results from both 4DCT scans will

be used by taking the geometric mean of the tissue elasticity measures of scan 1 and scan 2 at each time point.

Subjects will undergo a total of 7 research-ordered 4DCT scans: one at simulation, and two scans at each of the 3 post-radiation therapy time points (3, 6, and 12 months). Each 4DCT scan delivers approximately 75 mSv, which is the average value observed over 10 patients in our clinic using the newly installed Siemens Edge scanner. The Background Equivalent Radiation Time (BERT) is 25 years for each 4DCT scan, where the background radiation is assumed to be 3 mSv per year. To place this radiation exposure into further context, the radiation dose from the 7 research-ordered 4DCT scans (0.53 Gy) represents less than 1% of the radiation dose the patient will receive from their radiation therapy treatments. In an effort to make the radiation doses from the 4DCT scans “as low as reasonably achievable,” the radiation dose subjects receive for each 4DCT scan has recently been reduced by 2-3 times LOWER than prior care at UWHC. This reduction has been made possible by the improved radiation detection technology on the Siemens Edge CT scanner in Radiation Oncology. If further dose reduction can be accomplished by additional technologies or software development, these too will be implemented.

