Improving Pulmonary Function Following Radiation Therapy
NCT02843568

PI: [name]
Version Date: 6/9/2022

UW16037 Improving Pulmonary Function Following Radiation Therapy

Principal Investigator: [name], DABR, FAAPM
Director, Radiation Oncology Physics
Department of Human Oncology
University of Wisconsin Madison
Office: [contact]
[contact]

Co-Investigators:

[name]	[name]
[name]	[name]
[name]	[name]
[name]	[name]
[name]	[name]
[name]	
Collaborator [name], PhD	[name]
[name].	

Biostatistician: [name]
Professor
Depts. of Statistics and of Biostatistics & Medical Informatics

Data Manager: [name]
Clinical Coordinator
Department of Human Oncology
[contact]
[contact]

Improving Pulmonary Function Following Radiation Therapy

SCHEMA

All patients	Pre-RT 4DCT scans
All patients	Pre-RT weight, labs, morbidity scores, and PFTs

S T R A T I F Y	
Conventional Fractionation
 
60* subjects
 
(A total of 60-66 Gy, in daily fractions of 1.8-2.0 Gy/fx, nominally 5 fx/week)
 
Hypo-fractionation
 
60* subjects
 
Stereotactic body radiation therapy (40-60 Gy total, in 3-8 fx, using standard schemes at UWHCC) or 12Gy x 4 fx, 10Gy x 5 fx, 5Gy x 8 fx, or 20Gy x 3 fx
 
*To achieve primary objective, subjects must complete 3 month post RT assessments. If this does not occur, the subject will be replaced.
	R A N D O M I Z E	
Arm 1:
 
Create treatment plan that meets standard dose specifications
 
Arm 2:
 
Optimize treatment plan meet standard dose specifications and to minimize pulmonary function damage based on predictive model

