5.5. Radiation Therapy

The criteria and specifications below in sections 5.5.1 through 5.5.3 are applicable for both the standard of care arm (Arm 1) and the research arm (Arm 2), while those in section 5.5.4 are applicable to the research arm only.

5.5.1. Dose specification. Radiation doses between 60-66 Gy using standard fractionation (1.8-2.0 Gy/fx) and stereotactic body radiation therapy (SBRT) hypofractionation schemes used at UWHCC will be utilized. 60 subjects of each fractionation type (standard and hypofractionation) will be included. Treatment volumes will be at the discretion of the treating radiation oncologist and should follow standard of care at UWHC.

5.5.2. Treatment planning and target volumes. The critical structures will be in accordance with RTOG 0617.

5.5.3. Radiation dose limits for critical structures. Normal anatomy to be outlined on each CT image will include the lungs (right and left done separately), heart, skin, esophagus and spinal cord. Normal tissue constraints shall be prioritized in the following order for treatment planning: 1=spinal cord, 2=lungs, 3=esophagus, 4=brachial plexus, and 5=heart

Spinal Cord: The spinal cord dose limitation is the highest priority dose constraint and thus must be met irrespective of other constraints. Total “direct” plus “scatter” dose to the spinal cord must not exceed 50.5 Gy for standard fractionation. Doses for hypofractionation will follow recommendations in RTOG 0618, 0813, or 0915 based on fraction size.

Lungs: The dose-volume constraint to the lungs is the second highest priority and must be met, except if it conflicts with the cord dose constraints. For standard

fractionation, the volume of both lungs that receive more than 20 Gy (the V20) should not exceed 37% of the total. Alternatively, the mean lung dose should optimally be \leq 20 Gy. (By total lung volume we mean the total lung minus the CTV). Doses for hypofractionation will follow recommendations in RTOG 0618, 0813, or 0915 based on fraction size.

Brachial Plexus: Brachial plexus doses should be kept <66 Gy for standard fractionation. Doses for hypofractionation will follow recommendations in RTOG 0618, 0813, or 0915 based on fraction size.

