5.9. Duration of Therapy

Therapy will consist of 60-66 Gy in subjects receiving conventional radiation therapy and 40-60 Gy in subjects receiving SBRT. All therapeutic doses delivered on this protocol are consistent with standard of care radiation therapy dosing.

Subjects will have research 4DCT scans and research pulmonary functions performed 3, 6, and 12 months post completion of radiation therapy. These visits will coincide with the standard of care clinic visits which occur every 3 months during year one.

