6. DOSING DELAYS/DOSE MODIFICATIONS

Not applicable. If radiation dose needs to be modified or delayed, this is per standard of care and beyond the scope of this study. A note will be made in the study chart regarding any changes to radiation dose and any breaks in radiation therapy.

7. ADVERSE EVENTS:

The risks of harm for those subjects randomized to the research arm (arm 2) is equivalent to the control arm: optimized treatment plans in the research arm will be designed to meet the same dose specifications to organs-at-risk. In other words, when comparing the control and research arm:

- the same radiation doses will be delivered to the tumors
- the same radiation dose limits will be achieved for all normal tissues

There are minimal additional risks associated with the research procedures of 4DCT and PFT's.

The most significant risk from 4DCT is the increased radiation exposure which will be less than 1% of the dose received from the prescribed radiation therapy. Subjects may experience

discomfort from laying on their back during additional 4DCT scans. Each 4DCT scan will last 90 seconds. It is anticipated that patients will spend approximately 10-15 minutes on their back to position and collect the scans.

PFT's have the following associated risks: the test requires subjects to breathe in and out quickly, which may cause them to feel dizzy or faint. The test may increase the risk of asthma attack in those with asthma. In very rare cases, PFTs may cause a collapsed lung.

Patients will receive standard of care therapeutic radiation therapy dosing as part of this study. Toxicities associated with therapeutic radiation include: Reversible or permanent alopecia, bone marrow toxicity, skin reactions, and esophagitis are expected side effects of radiation therapy. Radiation-induced myocarditis or transverse myelitis rarely occur at doses lower than 50 Gy. Radiographic evidence of radiation change and subsequent fibrosis of the lung will occur within lung volume receiving first 6-12 months after initiation of treatment.

Acute (within 90 days post RT completion) and late radiation toxicities (> then 90 days post RT completion) will be recorded with special attention to the toxicities listed in appendix B and C. Any treatment interruption will be based on treating physician judgement and be documented as part of the study toxicity assessments.

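### Does the protocol understate the research 4DCT dose by calling it less than 1% of the therapy dose when SBRT can be prescribed at 40 Gy?

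*Combined protocol and SAP*

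**What the plan says.** Section 5.3 describes seven research-ordered scans per subject: one at simulation, and a pair at each of months 3, 6 and 12. It gives the dose per scan: "Each 4DCT scan delivers approximately 75 mSv, which is the average value observed over 10 patients in our clinic". It also expresses each scan as 25 years of background radiation at 3 mSv per year. For further context it adds that "the radiation dose from the 7 research-ordered 4DCT scans (0.53 Gy) represents less than 1% of the radiation dose the patient will receive" from treatment.

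Section 7 names radiation exposure as the leading risk of 4DCT and sizes it as "the increased radiation exposure which will be less than 1% of the dose received from the prescribed radiation therapy", without giving a number of scans.

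The prescriptions are set elsewhere. Section 5.9 gives 60-66 Gy for conventional fractionation and "40-60 Gy in subjects receiving SBRT". The Schema describes hypofractionation as "40-60 Gy total, in 3-8 fx, using standard schemes at UWHCC" and also names "12Gy x 4 fx, 10Gy x 5 fx, 5Gy x 8 fx, or 20Gy x 3 fx". Section 5.5.1 likewise says that "hypofractionation schemes used at UWHCC will be utilized", so the four named schemes are not a closed list.

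**The concern.** The percentage is stated for every subject, but its denominator runs from 40 to 66 Gy. A total of 0.53 Gy is below 1% only when the prescription is above 53 Gy, and three of the four SBRT schemes named in the Schema total less than that. The error is in the reassuring direction, and it concerns the only size that Section 7 attaches to what it treats as the main risk of the research scans. If a decision about acceptable exposure rested on the 1% mark, part of one stratum would have been assessed on a figure that does not apply to it.

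**Working it through.** **Inputs.** Scans: 1 + 2 × 3 = 7 (Section 5.3). Dose per scan: 75 mSv, an approximate mean over 10 patients with no spread given (Section 5.3). Prescriptions: 60-66 Gy conventional (Section 5.9). The schemes named in the Schema give 5 × 8 = 40, 12 × 4 = 48, 10 × 5 = 50 and 20 × 3 = 60 Gy.

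**The plan's own figures.** 7 × 75 mSv = 525 mSv, or 0.525, which rounds to the printed 0.53 Gy when mSv is read as mGy, as the protocol does. Background equivalent: 75 / 3 = 25 years per scan. Both reproduce.

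**Share of the prescription** = total scan dose / prescribed dose.

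| Prescription | 7 scans (0.525) | 7 scans (0.53 as printed) | 5 scans, through month 6 (0.375) |
|---|---|---|---|
| 40 Gy | 1.31% | 1.33% | 0.94% |
| 48 Gy | 1.09% | 1.10% | 0.78% |
| 50 Gy | 1.05% | 1.06% | 0.75% |
| 60 Gy | 0.88% | 0.88% | 0.63% |
| 66 Gy | 0.80% | 0.80% | 0.57% |

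The share equals 1% at 0.525 / 0.01 = 52.5 Gy (53 Gy with the printed total). Below that, the month 12 pair of scans carries the total past 1%.

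**Sensitivity to the scan dose.** Seven scans equal exactly 1% at 400 / 7 = 57.1 mSv per scan for 40 Gy, 480 / 7 = 68.6 mSv for 48 Gy, and 500 / 7 = 71.4 mSv for 50 Gy. Against 75 mSv these are reductions of 23.8%, 8.6% and 4.8%. At 48 and 50 Gy the excess is small enough that a modest error in an average over 10 patients would remove it. At 40 Gy it is not.

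**Section 7.** With no scan count, the sentence can be read per scan or cumulatively. One scan at 40 Gy is 0.075 / 40 = 0.19%. The cumulative reading is natural after Section 5.3, but it is an inference, so Section 7 is a related statement and not a second firm contradiction.

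**Who is affected.** The amendment dated 3/15/22 in Section 4.1 reports the hypofractionation cohort at 60 subjects and the conventional cohort at 46 of 60. The conventional prescriptions give 0.80% to 0.88%, so the statement is true for the stratum still below target. The mix of SBRT schemes is not given, so the number of subjects above 1% cannot be calculated.

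**The case for a change.** The best case for a correction is that a risk statement should be right at every dose the protocol permits, that this one errs towards reassurance, and that two phrases would repair it. The accrual point is also incomplete: SBRT subjects already enrolled are covered by the statement, some may still have had month 12 scans due, and the Schema and Section 11.1 provide for replacing subjects who miss the 3-month assessment.

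What stands is that the Section 5.3 sentence is inexact at 40 Gy and, on the nominal figures, slightly so at 48 and 50 Gy.

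What does not stand is that anything turns on it. The ratio compares different quantities, a scan dose stated in mSv and a tumour prescription in Gy, so neither the 1% mark nor a refined range around it is a meaningful limit. A reader who wants the exposure finds the scan count, the dose per scan, the total and the background equivalent in the same paragraph. Section 5.3 also reports that the scan dose had already been cut two- to three-fold and commits to adopting further reductions; it gives no lower figure, so this softens the point without answering it. The consent pages are not in the public document, so what subjects were told about the percentage cannot be judged here.

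**Conclusion.** The arithmetic behind the concern is right, and no change to the plan follows. For a subject with all seven scans the nominal share is 0.80% to 1.31% over 40-66 Gy, so about 1% describes it more accurately than a strict upper bound. The largest gap, at 40 Gy, is 0.31 percentage points, or 525 − 400 = 125 mSv, which is less than the dose of two scans. The gap is confined to SBRT prescriptions below about 53 Gy.

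This is a loosely worded context figure. The absolute doses are consistent with one another, and no endpoint, analysis, power figure, procedure, safety rule or trial conclusion depends on the percentage. The conclusion rests on the protocol's own conventions: mSv read as mGy, the prescribed dose as denominator, and 75 mSv taken as typical. It implies nothing about any prescription or about the scan schedule.

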5.4. Localization

Either portal imaging, daily cone beam, and/or optical surface tracking is acceptable for this study according to standard care. If cone beam imaging is prescribed by the treating radiation oncologist, the cone beam images will be utilized for correlative studies.

5.5. Radiation Therapy

The criteria and specifications below in sections 5.5.1 through 5.5.3 are applicable for both the standard of care arm (Arm 1) and the research arm (Arm 2), while those in section 5.5.4 are applicable to the research arm only.

5.5.1. Dose specification. Radiation doses between 60-66 Gy using standard fractionation (1.8-2.0 Gy/fx) and stereotactic body radiation therapy (SBRT) hypofractionation schemes used at UWHCC will be utilized. 60 subjects of each fractionation type (standard and hypofractionation) will be included. Treatment volumes will be at the discretion of the treating radiation oncologist and should follow standard of care at UWHC.

5.5.2. Treatment planning and target volumes. The critical structures will be in accordance with RTOG 0617.

5.5.3. Radiation dose limits for critical structures. Normal anatomy to be outlined on each CT image will include the lungs (right and left done separately), heart, skin, esophagus and spinal cord. Normal tissue constraints shall be prioritized in the following order for treatment planning: 1=spinal cord, 2=lungs, 3=esophagus, 4=brachial plexus, and 5=heart

Spinal Cord: The spinal cord dose limitation is the highest priority dose constraint and thus must be met irrespective of other constraints. Total “direct” plus “scatter” dose to the spinal cord must not exceed 50.5 Gy for standard fractionation. Doses for hypofractionation will follow recommendations in RTOG 0618, 0813, or 0915 based on fraction size.

Lungs: The dose-volume constraint to the lungs is the second highest priority and must be met, except if it conflicts with the cord dose constraints. For standard

fractionation, the volume of both lungs that receive more than 20 Gy (the V20) should not exceed 37% of the total. Alternatively, the mean lung dose should optimally be \leq 20 Gy. (By total lung volume we mean the total lung minus the CTV). Doses for hypofractionation will follow recommendations in RTOG 0618, 0813, or 0915 based on fraction size.

Brachial Plexus: Brachial plexus doses should be kept <66 Gy for standard fractionation. Doses for hypofractionation will follow recommendations in RTOG 0618, 0813, or 0915 based on fraction size.

Esophagus: The mean dose to the esophagus is optimally kept below 34 Gy.[47] This is not an absolute requirement, but is strongly recommended unless other, more critical constraints force the situation. The V60 (% volume of esophagus exceeding 60 Gy) should be calculated for each patient for standard fractionation. Doses for hypofractionation will follow recommendations in RTOG 0618, 0813, or 0915 based on fraction size.

Heart: The following limits are recommended: 60 Gy to $<1/3$, 45 Gy to $<2/3$, and 40 Gy to $<100\%$ of the heart for standard fractionation. Doses for hypofractionation will follow recommendations in RTOG 0618, 0813, or 0915 based on fraction size.

5.5.4. Research Arm (Arm 2) Only - Planning strategy to reduce pulmonary function damage.

Subjects in the second arm will also receive treatment plans that meet all the criteria of the first arm, but their treatment plans will include strategies to reduce pulmonary function damage following radiation therapy. The strategy to reduce pulmonary function damage, described below, will be implemented during treatment planning. In brief, radiation dose distributions will be designed to “redistribute” the radiation dose away from lung regions with high tissue elasticity. Lung tissue elasticity is calculated from measures of tissue expansion that occurs during respiration. Specifically, the Jacobian determinant of the transformation matrix between the CT scan acquired when the subject has reached the end of exhale and the scan acquired when the subject has reached the end of inhale. These images, which are extracted from the 4DCT data, allow the creation of lung tissue elasticity maps like the ones shown in Figure 3 below.

[figure not shown]

Figure 3. Map of lung tissue elasticity, where a Jacobian value of 1.0 (green) indicates no tissue expansion. The higher the Jacobian value (red end of scale) the greater tissue expansion.

Subjects randomized to this arm of the trial will have the same prescribed radiation dose to the tumor volume and held to the same radiation dose criteria as the subjects in the standard of care arm. The fundamental difference will be radiation doses for these subjects will be redistributed away from regions predicted to cause the greatest reduction in pulmonary function if damaged. For example, to treat the tumor in the images above (slightly medial to the dashed blue lines), circumferential radiation beams restricted to the lower lobes of the lung (green regions) would be chosen over beams that enter or exit the higher tissue expansion regions of the right middle lobe or right upper lobe (blue & purple regions).

Pre-radiation therapy 4DCT images (Section 5.3.1) will be used to identify regions-of-interest (ROI) uniquely utilized in this planning strategy. These ROIs including anatomical regions (airway tree, pulmonary vasculature, heart, and lobar regions of the lung) and functional regions (regions of the lung discretized by the amount of tissue expansion that occurs during ventilation). Although tissue expansion is determined at a 1mm^3 resolution, the ROIs will be grouped in 0.05 bins of expansion (typically from 1.05 up to 1.5). Airway tree branches and pulmonary vasculature supporting lung regions of high tissue expansion will be preferentially avoided as well. Radiation therapy treatment planning will be calculated using an inverse optimization technique, relying on dose objectives specified for each ROI. The penalty or “cost function” for failing to meet the specified dose objective will increase linearly with radiation dose, while the weight for each cost function will be determined from the slope of the dose response curve for each ROI. The inverse optimization algorithm will minimize the sum of the cost functions for all dose objectives created in the treatment plan. These dose objectives will be added to the dose objectives utilized in the conventional arm of this study (Sections 5.5.1 – 5.5.3).

5.6. Chemotherapy

Chemotherapy is at the discretion of the treating physician and will follow standard of care. The chemotherapeutic agents, dosing and the number of cycles during and after RT will be recorded.

5.7. Study Procedures and Walkthrough

- 5.7.1. **Radiation therapy planning simulation.** RT simulation will consist of 4DCT imaging as per Department of Human Oncology's standard of care. A second research 4DCT will be acquired at this time point.
- 5.7.2. **Pulmonary function tests.** The subject will be sent to the pulmonary function lab for spirometry, and DLCO. The pulmonary function tests may be done on the same day, but must be completed before the subject receives the first fraction of radiation therapy.
- 5.7.3. **Dosimetric planning.** Performed according to standard of care.
- 5.7.4. **Treatment.** Subjects will be treated once daily or every other day if receiving SBRT. The respiratory surrogate systems will be used daily during radiation therapy treatment per standard clinical practice to monitor respiratory motion.
- 5.7.5. **Post-treatment 4DCTs.** Three more 4DCT imaging sets will be obtained, at 3 months, 6 months, and 12 months after the last radiation treatment (10 week window: – 2 weeks/+8weeks). These 4DCT must be performed on the Radiation Oncology Siemens Edge. These are research-designated 4DCTs and will not be used for clinical care.
- 5.7.6. **Post-treatment PFT.** Subjects will undergo PFT at the 3 month, 6 month, and the 12 month imaging to obtain spirometric, and DLCO measurements. These will be performed for research purposes.
- 5.7.7. **Follow-up.** Subjects will have follow-up appointments with their radiation oncologist every 3 months for the first year, every 4 months for year two, and every 6 months for years 3-5. Follow-up mirrors that of RTOG-0117, enabling time-point comparisons. Data to be collected are outlined in section 11 (measurement of effect). The follow-up time points are consistent with standard of care post radiation disease monitoring.

